8.2.2 Reporting

To ensure patient safety, every SAE, regardless of suspected causality, occurring after the patient has provided informed consent and until at least 30 days after the patient has stopped study treatment must be reported to Novartis within 24 hours of learning of its occurrence.

Any additional information for the SAE including complications, progression of the initial SAE, and recurrent episodes must be reported as follow-up to the original episode within 24 hours of the investigator receiving the follow-up information. An SAE occurring at a different time interval or otherwise considered completely unrelated to a previously reported one should be reported separately as a new event.

Any SAEs experienced after the 30 day safety evaluation follow-up period should only be reported to Novartis if the investigator suspects a causal relationship to the study treatment.

Information about all SAEs is collected and recorded on the Serious Adverse Event Report Form; all applicable sections of the form must be completed in order to provide a clinically thorough report. The investigator must assess and record the relationship of each SAE to each specific study treatment (if there is more than one study treatment), complete the SAE Report Form in English, and submit the completed form within 24 hours to Novartis. Detailed instructions regarding the SAE submission process and requirements for signatures are to be found in the investigator folder provided to each site.

Each re-occurrence, complication, or progression of the original event should be reported as a follow-up to that event regardless of when it occurs. The follow-up information should describe whether the event has resolved or continues, if and how it was treated, whether the blind was broken or not, and whether the patient continued or withdrew from study participation.

[figure not shown]
If the SAE is not previously documented in the Investigator's Brochure or Package Insert (new occurrence) and is thought to be related to the Novartis study treatment, an oncology Novartis Chief Medical Office and Patient Safety (CMO&PS) department associate may urgently require further information from the investigator for Health Authority reporting. Novartis may need to issue an Investigator Notification (IN), to inform all investigators involved in any study with the same drug that this SAE has been reported. Suspected Unexpected Serious Adverse Reactions (SUSARs) will be collected and reported to the competent authorities and relevant ethics committees in accordance with Directive 2001/20/EC or as per national regulatory requirements in participating countries.

8.3 Emergency unblinding of treatment assignment

Not applicable.

8.4 Pregnancies

To ensure patient safety, each pregnancy occurring while the patient is on study treatment must be reported to Novartis within 24 hours of learning of its occurrence. The pregnancy should be followed up to determine outcome, including spontaneous or voluntary termination, details of the birth, and the presence or absence of any birth defects, congenital abnormalities, or maternal and/or newborn complications.

Pregnancy should be recorded on a Clinical Trial Pregnancy Form and reported by the investigator to the oncology Novartis Drug Safety and Epidemiology Department (DS&E). Pregnancy follow-up should be recorded on the same form and should include an assessment of the possible relationship to the study treatment any pregnancy outcome. Any SAE experienced during pregnancy must be reported on the SAE Report Form.

Pregnancy outcomes until delivery must be collected for the female partners of any males who took study treatment in this study. Consent to report information regarding these pregnancy outcomes should be obtained from the mother.

8.5 Warnings and precautions

No evidence available at the time of the approval of this study protocol indicated that special warnings or precautions were appropriate, other than those noted in the provided Investigator Brochure. Additional safety information collected between IB updates will be communicated in the form of Investigator Notifications. This information will be included in the patient informed consent and should be discussed with the patient during the study as needed.

8.6 Data Monitoring Committee

This study will institute a data monitoring committee (DMC) which will function independently of all other individuals associated with the conduct of this clinical trial, including the site investigators participating in the study. The DMC will be constituted prior to the randomization of the first patient. The DMC will be responsible to review safety data at approximately 6 months after the first randomized patient has started study treatment. Subsequent reviews will be conducted approximately every 6 months on an as and when needed basis thereafter (ie. if significant safety findings are noted). This includes but does not limit the role of the DMC to evaluate these data and to provide recommendations to the sponsor to continue, modify or stop the study early. The DMC will be in place at least until the conduct of the primary analysis.

[figure not shown]
It is expected that the DMC will consist at a minimum of two physicians with appropriate disease area qualifications and one statistician. There will be a meeting with the DMC describing their roles and responsibilities and discussing potential data format and process issues prior to the finalization of DMC charter.

It is envisioned that the DMC may make certain types of recommendations, namely:

- No safety concerns, ethical to continue the study as planned
- Serious safety concerns precluding further study treatment, regardless of efficacy
- Recommendation to continue the study but proposing an amendment to the protocol (e.g., incorporate an additional safety assessments)

8.7 Steering Committee

In order to monitor study conduct, a Steering Committee (SC) will be established comprising investigators participating in the trial. Additionally two sponsor representatives (a physician and a statistician) will be active members of this committee.

The SC will ensure transparent management of the study according to the protocol through recommending and approving modifications as circumstances require. Novartis will make final decisions on trial conduct based on SC recommendations. Together with the clinical trial team, the SC will review protocol amendments as appropriate, and also develop recommendations for publications of study results including authorship rules. The details of the role of the Steering Committee will be defined in a Steering Committee charter.

9 Data collection and management

9.1 Data confidentiality

Information about study subjects will be kept confidential and managed under the applicable laws and regulations. Those regulations require a signed subject authorization informing the subject of the following:

- What protected health information (PHI) will be collected from subjects in this study
- Who will have access to that information and why
- Who will use or disclose that information
- The rights of a research subject to revoke their authorization for use of their PHI.

In the event that a subject revokes authorization to collect or use PHI, the investigator, by regulation, retains the ability to use all information collected prior to the revocation of subject authorization. For subjects that have revoked authorization to collect or use PHI, attempts should be made to obtain permission to collect follow-up safety information (e.g. has the subject experienced any new or worsened AEs) at the end of their scheduled study period.

The data collection system for this study uses built-in security features to encrypt all data for transmission in both directions, preventing unauthorized access to confidential participant information. Access to the system will be controlled by a sequence of individually assigned user identification codes and passwords, made available only to authorized personnel who have completed prerequisite training.

Prior to entering key sensitive personally identifiable information (Subject Initials and exact Date of Birth), the system will prompt site to verify that this data is allowed to be collected. If the site indicates that country rules or ethics committee standards do not permit collection of these items, the system will not solicit Subject Initials. Year of birth will be solicited (in the place of exact date of birth) to establish that the subject satisfies protocol age requirements and to enable appropriate age-related normal ranges to be used in assessing laboratory test results.

9.2 Site monitoring

Before study initiation, at a site initiation visit or at an investigator's meeting, Novartis personnel (or designated CRO) will review the protocol and eCRFs with the investigators and their staff. During the study, the field monitor will visit the site regularly to check the completeness of patient records, the accuracy of entries on the eCRFs, the adherence to the protocol to Good Clinical Practice, the progress of enrollment, and to ensure that study

treatment is being stored, dispensed, and accounted for according to specifications. Key study personnel must be available to assist the field monitor during these visits.

The investigator must maintain source documents for each patient in the study, consisting of case and visit notes (hospital or clinic medical records) containing demographic and medical information, laboratory data, electrocardiograms, and the results of any other tests or assessments. All information recorded on eCRFs must be traceable to source documents in the patient's file. The investigator must also keep the original signed informed consent form (a signed copy is given to the patient).

The investigator must give the monitor access to all relevant source documents to confirm their consistency with the eCRF entries. Novartis monitoring standards require full verification for the presence of informed consent, adherence to the inclusion/exclusion criteria and documentation of SAEs. Additional checks of the consistency of the source data with the eCRFs are performed according to the study-specific monitoring plan.

9.3 Data collection

For studies using Electronic Data Capture (EDC), the designated investigator staff will enter the data required by the protocol into the Electronic Case Report Forms (eCRF). The eCRFs have been built using fully validated secure web-enabled software that conforms to 21 CFR Part 11 requirements, Investigator site staff will not be given access to the EDC system until they have been trained. Automatic validation programs check for data discrepancies in the eCRFs and, allow modification or verification of the entered data by the investigator staff.

The Principal Investigator is responsible for assuring that the data entered into eCRF is complete, accurate, and that entry and updates are performed in a timely manner.

Data collected by third parties (biochemistry, PCR assessments, biomarkers, PK) will be sent electronically to Novartis.

[figure not shown]
9.4 Database management and quality control

For studies using eCRFs, Novartis personnel (or designated CRO) will review the data entered by investigational staff for completeness and accuracy. Electronic data queries stating the nature of the problem and requesting clarification will be created for discrepancies and missing values and sent to the investigational site via the EDC system. Designated investigator site staff are required to respond promptly to queries and to make any necessary changes to the data.

Concomitant treatments and prior medications entered into the database will be coded using the WHO Drug Reference List, which employs the Anatomical Therapeutic Chemical classification system. Medical history/current medical conditions and adverse events will be coded using the Medical dictionary for regulatory activities (MedDRA) terminology.

Samples and/or data will be processed centrally and the results will be sent electronically to Novartis (or a designated CRO).

Randomization codes and data about all study treatments dispensed to the patient and all IRT assigned dosage changes will be tracked using the Novartis Interactive Response Technology.

For EDC studies, after database lock, the investigator will receive a CD-ROM or paper copies of the patient data for archiving at the investigational site.

10 Statistical methods and data analysis

The data will be analyzed by Novartis and/or designated CRO. It is planned that the data from participating centers in this protocol will be combined, so that an adequate number of patients will be available for analysis.

Study data will be summarized with respect to demographic and baseline characteristics, efficacy observations and measurements, safety observations and measurements, and all relevant PK and PD measurements.

The cut-off date for the primary analysis is defined as the date when all patients have been on study for 24 weeks or early discontinued. The cut-off date for the final treatment phase analysis is defined as 30 days after last patient last study drug to ensure that all available treatment phase data from all patients up to the last dose of study drug taken in this study, will be analyzed and summarized in a final treatment phase CSR. Patients will be further followed up for survival and progression for up to 5 years from the date the last patient received the first study dose. An update analysis of OS and PFS will be performed at the end of the follow-up period.

10.1 Analysis sets

10.1.1 Full Analysis Set

The **Full Analysis Set (FAS)** comprises all patients to whom study treatment has been assigned by randomization. According to the intent to treat principle, patients will be analyzed according to the treatment and stratum they have been assigned to during the randomization procedure.

10.1.2 Safety set

[figure not shown]
The **Safety Set** includes all patients who received at least one dose of study treatment. Patients will be analyzed according to the study treatment received, where treatment received is defined as the randomized treatment if the patient took at least one dose of that treatment or the first treatment received if the randomized treatment was never received.

10.1.3 Per-Protocol set

The **Per-Protocol Set (PPS)** consists of a subset of the patients in the FAS who are compliant with requirements of the CSP. The PPS will be used for sensitivity analyses on the primary endpoint only.

Oncology standards for protocol deviations potentially leading to exclusion from the PPS are:

- Type of indication different from those required by the CSP
- If prior therapy does not match with CSP requirements in terms of number and types of previous therapy regimens

- Another anti-neoplastic therapy administered after start of study treatment and prior to first efficacy assessment
- Study treatment received different from treatment assigned by randomization

10.1.4 Dose-determining analysis set

Not applicable.

10.1.5 Pharmacokinetic analysis set

The **Pharmacokinetic analysis set (PAS)** includes all patients who provide at least one evaluable PK concentration. For a concentration to be evaluable, patients are required to:

- Take a dose of ABL001 prior to sampling,
- Take the same dose of ABL001 for at least 3 consecutive days without dose interruption or dose modification prior to sampling,
- For post-dose samples, do not vomit within 4 hours after the dosing of ABL001; For pre-dose samples do not vomit within 4 hours after the dosing of ABL001 prior to sampling,
- Have the pre-dose sample collected before the next dose administration

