4.1 Description of study design

The study is a phase 3, multi-center, open-label randomized study of oral ABL001 versus bosutinib in patients with Chronic Myelogenous Leukemia in chronic phase (CML-CP), previously treated with 2 or more tyrosine kinase inhibitors.

The trial is designed to compare the efficacy and safety of ABL001 with that of bosutinib in the treatment of patients with CML-CP having previously been treated with a minimum of two prior ATP-binding site TKIs with a BCR-ABL ratio-IS $\geq 1\%$ at screening.

The study will also investigate secondary endpoints for efficacy, safety and PK of single-agent ABL001 compared to bosutinib. Tolerability, PK, PRO and exploratory biomarker activities will also be assessed.

Patients meeting all of the inclusion and none of the exclusion criteria will be randomized into one of the 2 treatment arms, based on a 2:1 randomization between the ABL001 arm and the bosutinib arm.

[figure not shown]
The randomization will be stratified to ensure the study population is balanced between the arms with respect to cytogenetic response status (See [Section 7.2.1.2](#)) at screening as follows:

- Major Cytogenetic response (complete or partial)
- No major cytogenetic response (minor, minimal or none)

Patients will continue to receive the assigned study treatments (ABL001 or bosutinib) for up to 96 weeks after the last patient received the first study dose i.e., patients who are benefiting from their study treatment can continue to receive the treatment for up to a period of approximately 2 years following the completion of study enrollment. Patients who discontinue their study treatment at any time during the study will be followed up for survival and for progression to AP/BC for up to 5 years from the date the last patient received the first study dose.

Serial PK samples over 12 hours will be collected on Week 2 Day 1 from at least 20 CML-CP patients (full PK group) on the ABL001 arm, in addition to trough PK samples. These patients will be identified sequentially at selected sites that are capable of serial PK sampling over 12 hours. In the remaining patients in the ABL001 arm, sparse post-dose PK samples on Week 1 Day 1 and trough PK samples will be collected (sparse PK group).

Figure 4-1 Schematic of Study Design

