7.2.3 Pharmacokinetics

Blood samples for ABL001 pharmacokinetics will be collected on all study subjects allocated to the ABL001 treatment arm. Blood samples for full PK profiles will be collected from at least 20 patients. These patients will be identified sequentially at selected sites that are capable of serial PK sampling over 12 hours. ABL001 should be taken for at least 3 consecutive days without interruption or dose modification prior to full PK day.

For the assessment of ABL001 pharmacokinetics in plasma, serial blood samples will be collected following ABL001 administration at several time-points (see [Table 7-7](#) and [Table 7-8](#) below for further details). Remaining plasma samples may be used for identification and/or measurement of metabolites of ABL001.

Refer to the [\[CABL001A2301 Laboratory Manual\]](#) for detailed instructions for the collection, handling, and shipment of PK samples.

Table 7-7 Pharmacokinetic blood collection log (Sparse PK-group-ABL001 arm)

Week	Day	Scheduled Time Point	Dose Reference ID	PK Sample No	Blood Volume (mL)
1	1	2 h (± 10 min)	101	101	2
2	1	0 h (Pre-dose) ^a	102/2001 ^b	102	2
	1	2 h (± 10 min)	102	103	2
	1	3 h (± 15 min)	102	104	2
	1	4 h (± 15 min)	102	105	2
4	Any	0 h (Pre-dose) ^a	103/3001 ^b	106	2
12	Any	0 h (Pre-dose) ^a	104/4001 ^b	107	2
24	Any	0 h (Pre-dose) ^a	105/5001 ^b	108	2
96	Any	0 h (Pre-dose) ^a	106/6001 ^b	109	2
		Unscheduled		1001+	

^a Pre-dose PK sample should be taken immediately prior to the next administration of ABL001. PK samples on Week 2 Day 1 should be taken before and after the morning dose (i.e. 1st dose of the day). PK samples on other weeks may be taken immediately prior to the morning dose (i.e. 1st dose of the day) or the evening dose (i.e. 2nd dose of the day).

^b The first dose reference ID refers to the first dose administered after PK sampling and the second dose reference ID refers to the last dose administered prior to the PK sampling.

[figure not shown]

Table 7-8 Pharmacokinetic blood collection log (Full PK group-ABL001 arm)

Week	Day	Scheduled Time Point	Dose Reference ID	PK Sample No	Blood Volume (mL)
1	1	2 h (± 10 min)	1	1	2
2	1	0 h (Pre-dose) ^a	2/201 ^b	2	2
	1	0.5 h (± 10 min)	2	3	2
	1	1 h (± 10 min)	2	4	2
	1	2 h (± 10 min)	2	5	2
	1	3 h (± 15 min)	2	6	2
	1	4 h (± 15 min)	2	7	2
	1	6 h (± 30 min)	2	8	2
	1	8 h (± 60 min)	2	9	2
	1	12 h (± 60 min) (Pre-dose) ^a	3/2 ^b	10	2
4	Any	0 h (Pre-dose) ^a	4/401 ^b	11	2
12	Any	0 h (Pre-dose) ^a	5/501 ^b	12	2

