10.5.4 Secondary PK objectives

The PK objective is to characterize the PK of ABL001 in CML population.

Using PAS, summary statistics (n, mean, SD, coefficient of variation (CV) for mean, geometric mean, CV for geometric mean, median, minimum and maximum) will be presented for plasma concentration at each scheduled time point. The geometric mean with mean (SD) and individual plasma concentration versus time profiles of ABL001 will be displayed graphically.

Using Safety set, concentration data will be listed. Concentration values below the limit of quantification (BLQ) will be set to zero by the Bioanalyst and displayed in listings as zero

with a flag. BLQ values will be handled as zero in any calculations of summary statistics, but handled as missing for the calculation of the geometric means and CVs.

Pharmacokinetic parameters will be determined by non-compartmental method(s) using the pharmacokinetic profile of ABL001 in patients with full PK sampling. PK parameters listed in [Table 10-1](#) will be derived and reported, when feasible.

Population PK modeling may be performed and the results may be reported in a separate population PK report. Data from this study may be combined with data from other studies for this analysis.

Table 10-1 Non compartmental pharmacokinetic parameters in full PK group

AUC _{0-12h}	The area under the plasma concentration-time curve from time zero to 12 h (mass x time x volume ⁻¹) ^a
C _{max}	The maximum (peak) observed plasma drug concentration after dose administration (mass x volume ⁻¹)
T _{max}	The time to reach maximum (peak) plasma drug concentration after dose administration (time)
CL/F	The total body clearance of drug from the plasma after oral administration (volume x time ⁻¹)

[figure not shown]

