Serial PK samples over 12 hours will be collected on Week 2 Day 1 from at least 20 CML-CP patients (full PK group) on the asciminib arm, in addition to trough PK samples. These patients will be identified sequentially at selected sites that are capable of serial PK sampling over 12 hours. In the remaining patients in the asciminib arm and in patients that have switched to asciminib, sparse post-dose PK samples on Week 1 Day 1 and trough PK samples will be collected (sparse PK group).

Figure 4-1 Schematic of Study Design

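### The PK evaluability rule in Section 10.1.5 (Amendment 1 text) can never be met by the scheduled Week 1 Day 1 sample, in conflict with Sections 7.2.3 and 10.5.4

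*Combined protocol and SAP*

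**What the plan says.** Section 10.1.5 (Amendment 1 protocol) defines the PAS as the set that "includes all patients who provide at least one evaluable PK concentration". It then sets joint conditions, introduced by "For a concentration to be evaluable, patients are required to". The second of these is "Take the same dose of ABL001 for at least 3 consecutive days without dose interruption or dose modification prior to sampling". The conditions distinguish pre-dose from post-dose samples where vomiting is concerned, but the 3-day condition is not limited to any visit or sample type.

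The sampling plan includes a first-dose sample. Section 4.1 says of the sparse group that "sparse post-dose PK samples on Week 1 Day 1 and trough PK samples will be collected". Table 7-7 (sample 101) and Table 7-8 (sample 1) both place a 2 h post-dose sample on Week 1 Day 1, so both PK groups have it. The serial profile comes a week later: "Serial PK samples over 12 hours will be collected on Week 2 Day 1 from at least 20 CML-CP patients (full PK group".

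Two other sections bear on the scope of the rule. Section 7.2.3 gives the 3-day condition as "ABL001 should be taken for at least 3 consecutive days without interruption or dose modification prior to full PK day", which attaches it to the serial profile day. Section 10.5.4 says that, using the PAS, summary statistics "will be presented for plasma concentration at each scheduled time point".

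**The concern.** A condition suited to steady-state samples has been written as a condition on every concentration. The Week 1 Day 1 sample is taken on the first day of dosing, so three days of prior dosing are impossible. The plan therefore schedules a sample that its own definition rules out, and then promises a summary at that time.

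The stake is modest. Either the programmer applies the definition and the Week 1 Day 1 row is empty, or the programmer fills the row on the strength of a choice that the plan does not document. A patient who stops before Week 2 Day 1 has only the first-dose sample, provides no evaluable concentration and drops out of the PAS. Characterising ABL001 pharmacokinetics is a secondary objective, so how this sample is handled should be settled in the plan.

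**Working it through.** The plan states no figure to reproduce here. The check sets the rule against the schedule and counts the samples affected.

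**Inputs**
- Required prior dosing: at least 3 consecutive days at the same dose (Section 10.1.5).
- Sparse schedule (Table 7-7): Week 1 Day 1, 1 sample; Week 2 Day 1, 4; Weeks 4, 12, 24 and 96, 1 each.
- Full schedule (Table 7-8): Week 1 Day 1, 1 sample; Week 2 Day 1, 9; Weeks 4, 12, 24 and 96, 1 each.
- ABL001 arm: 148 patients (Section 10.8).
- Full PK group: at least 20 patients (Sections 4.1 and 7.2.3).

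**Prior dosing days at each visit** (study day minus 1, or study day if the sampling day is counted)
- Week 1 Day 1 is day 1: 1 − 1 = 0, or 1 with the sampling day. Both are below 3, so the sample fails on either reading, for every patient.
- Week 2 Day 1 is day 8: 8 − 1 = 7. This passes if dosing was not interrupted or modified in the days before. Later visits can pass in the same way.

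**Share of scheduled samples that fail by rule**
- Sparse: 1 + 4 + 4 = 9 samples, of which 1 fails (1/9 = 11.1%).
- Full: 1 + 9 + 4 = 14 samples, of which 1 fails (1/14 = 7.1%).
- Whole arm, assuming the minimum of 20 in the full group and so 128 in the sparse group: 128 × 9 + 20 × 14 = 1,152 + 280 = 1,432 scheduled samples. 148/1,432 = 10.3%. With more full-PK patients the share moves down towards 7.1%.
- Of the Week 1 Day 1 samples themselves, all 148 fail.

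These are scheduled samples; missed visits and unscheduled samples are not counted.

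**Side by side.** Section 10.1.5 applies the 3-day condition to any concentration, Section 7.2.3 applies it before the full PK day, and Section 10.5.4 expects a summary at every scheduled time, including Week 1 Day 1. A literal reading of the first is compatible with neither of the others.

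**The case against.** The strongest objection is about version. The rule quoted is the Amendment 1 text. The file also contains the Amendment 3 protocol, but the text available stops before its Section 10, so the wording now in force cannot be read. The Amendment 2 change list says that Section 10.1.5 was revised, for pre-dose and post-dose samples and vomiting. This objection stands and limits confidence. It does not dispose of the point: neither the Amendment 2 nor the Amendment 3 change list reports removal of the 3-day condition, and the Amendment 3 protocol keeps the Week 1 Day 1 sample in Section 4.1 and Table 7-1.

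Second, the PAS is a set of patients. Section 10.5.4 does not expressly say that a non-evaluable value is dropped for a patient who is otherwise in the PAS. That is correct. The empty row follows only if non-evaluable values are excluded, which is the natural purpose of defining evaluability but is not stated.

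Third, the intended scope can be recovered. Section 7.2.3 refers only to the full PK day, and the Amendment 1 change summary explains the 3-day figure for Section 10.1.5 in the same terms. This shows what was probably meant. It also confirms that the operative definition is broader than the intent.

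A reader might go further and infer three things that the documents do not support:
- That the samples are wasted. Section 10.5.4 lists concentrations on the Safety set and allows population PK modelling. Section 10.6.2 allows exposure-response analyses, including for ECG, and Table 7-5 has an ECG at the same 2 h time on Week 1 Day 1.
- That a first-dose versus Week 2 comparison is lost. None is planned.
- That patients who switch from bosutinib add to the count. The switch came in with Amendment 3, and nothing visible says whether those patients enter the PAS. Counting them would apply the Amendment 1 rule to a later design.

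**Conclusion.** The conflict is real on the Amendment 1 text and needs no assumption beyond a literal reading: the Week 1 Day 1 2 h sample cannot be evaluable under Section 10.1.5. It affects 1 of 9 scheduled samples per sparse-PK patient, 1 of 14 per full-PK patient, and about 148 samples in the ABL001 arm if 148 patients are randomized to it and each is sampled as scheduled.

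The consequences are limited to the PAS and its concentration summaries. The empty row depends on non-evaluable values being excluded. Loss from the PAS concerns only patients whose sole sample is Week 1 Day 1; the documents give no number for them. AUC0-12h, Cmax, Tmax and CL/F come from the Week 2 Day 1 profile and are untouched, as are trough concentrations, Safety-set listings, any population PK model and all efficacy results.

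Severity is minor. Confidence is moderate, because the rule has probably persisted into Amendment 3 but this is not confirmed.

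**What to change.** First check Section 10.1.5 of the Amendment 3 protocol. If the 3-day condition is still unrestricted, limit it to samples from Week 2 Day 1 onward, and state that the Week 1 Day 1 sample is evaluable if the first dose was taken before sampling and there was no vomiting within 4 hours of that dose. Align Section 7.2.3 with this wording. In Section 10.5.4, say whether non-evaluable values of PAS members are left out of the summaries.

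The cost is a sentence in the analysis-set definition and a matching clarification in the other two sections. No patient procedure, sampling time, sample size or test changes.
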